#### **Hypothesis or Research Question**

We hypothesize that surgical complication rates are higher at certain times during the year than others. Specifically;

Primary hypothesis: Perioperative morbidity will be highest toward the end of the calendar year (December) corresponding with insurance deductible year-end.

Secondary hypothesis: Perioperative morbidity will be high as well with the start of academic trainees (July).

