Patients who meet their insurance deductibles are likely more eager to proceed with an elective procedure, as they will little or no out of pocket cost. Many physician practices notice a surge of patients seeking care at the end of the year compared to other times of the year. Patients who have met their deductible likely utilize more healthcare resources because they have more health problems, or have had more procedures performed during that year. Thus there may be potential for sicker and more complicated patients to undergo surgery at the end of the year as compared to other times of the year. These patients may suffer more surgical complications that could then lead to an overall greater cost for healthcare. If so, this difference could impact future health care policy and rationing of resources.

Surgeon related factors that contribute to perioperative morbidity have also become increasingly important and some authors have evaluated these possible factors. Surgeon related factors that have been studied include surgeon volume, surgeon workload per day, procedure timing, and trainee participation. One study found that low-volume surgeons have a higher risk of complications than high-volume surgeons [6]. Hsu and colleagues found that patients receiving an implantable cardioverter-defibrillator implant in the afternoon/evening and on weekends or holidays had higher rates of adverse events [7]. The total number of hours a surgeon operates per day was found to be independently associated with an increased risk of complications when performing pulmonary lobectomies [8]. Trainee participation has been associated with major complications in vaginal hysterectomy and with minor complications in all routes of hysterectomy [9].

Prior studies have often evaluated the “July effect” which is the beginning of a new academic year at teaching hospitals. This time of the year is important, as it is when trainees are moving up in their roles involving patient care and taking on more responsibility. Not only are new interns involved in patient care but trainees at all levels are in participating in a new role. Recently graduated senior residents are now in attending surgeon positions. Findings have

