### **Research Plan**

- **Study Design**
  - Retrospective cohort study using Electronic Privacy Identification Center (EPIC) database
- **Setting for the study**
  - Good Samaritan and Bethesda North Hospitals
- **Participants**
  - *Describe*
    - All patients 18 years and older who underwent a surgical procedure in the main operating rooms at Good Samaritan Hospital and Bethesda North Hospital between January 1, 2015 and December 31, 2016.
    - Approximately 9,000 cases are performed annually at the Good Samaritan Hospital main OR and 15,000 cases are performed annually at the Bethesda North main OR.
  - *Inclusion criteria*
    - All persons aged 18 and older undergoing surgical procedures in the main operating room during the study period
  - *Exclusion criteria*
    - Patients under the age of 18
    - Procedures done outside of the main operating suites (Endoscopy suite, Labor and Delivery)
  - *Sample Size*
    - About 48,000 chart review is expected.
- **Data Collection**
  - Basic demographics and surgical procedure data will be collected.

- Date of surgery, surgery location, and surgeon name will be collected.
- Trainee participation will be recorded – resident or fellow participation in case.
- Patient comorbidities will be collected including but not limited to obesity, tobacco use, ASA classification, DM, HTN, heart disease, pulmonary disease, chronic kidney disease, prior surgical history in past 6 months, preoperative lab data.
- Intraoperative surgical complications and hospital length of stay will be collected.
- Insurance information will be collected
- Postoperative complications including but not limited to reoperation, readmission within 90 days of surgery for any reason, death within 90 days will be collected. Complications inherent to most surgical procedures including excessive blood loss, need for blood transfusion, infection, thromboembolic events, and injury to surrounding organs will be collected.

- **Intervention or experimental aspect of the study**
  - Not applicable as it is a retrospective chart review
- **Statistical Analysis**

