  - Descriptive statistics will be calculated for demographics, preoperative, and intraoperative information. Chi-squared tests will be employed for categorical variables and t test or Mann-Whitney U test for continuous variables. Mean (SD) values will be used for data meeting the assumptions for normality; median (IQR) values will be used for data not meeting the assumptions for parametric procedures. Multivariate logistic regression model will be implemented for a prediction model.

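### The Statistical Analysis section specifies no analysis that estimates the December (primary) or July (secondary) hypothesis

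*Combined protocol and SAP*

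**What the plan says.** The Hypothesis or Research Question section gives the primary hypothesis as "Perioperative morbidity will be highest toward the end of the calendar year (December) corresponding with insurance deductible year-end" and the secondary as "Perioperative morbidity will be high as well with the start of academic trainees (July". It names no comparison months for either.

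The Statistical Analysis part of the Research Plan is four sentences long. It promises descriptive statistics for demographic, preoperative and intraoperative data and says when means or medians are used. Its tests are set by variable type: "Chi-squared tests will be employed for categorical variables and t test or Mann-Whitney U test for continuous variables". It closes with "Multivariate logistic regression model will be implemented for a prediction model". It mentions no month, morbidity outcome, reference period, covariate or significance level.

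The Data Collection part supplies raw material: "Date of surgery, surgery location, and surgeon name will be collected", and "Postoperative complications including but not limited to reoperation, readmission within 90 days of surgery for any reason, death within 90 days will be collected". It also lists blood loss, transfusion, infection, thromboembolism and organ injury. The list is open-ended, and no item or combination is designated as perioperative morbidity.

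**The concern.** A primary hypothesis needs an outcome, two groups to compare and an estimate that carries the test. None of these is stated. The t and Mann-Whitney tests imply two groups, but the groups are not named. A prediction model is judged by how well it predicts. It would yield a December odds ratio only if month were entered, and the plan does not say that it is.

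The gap matters because the candidate analyses ask different questions:

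- December against all other months puts July in the comparator, although the secondary hypothesis expects July to be raised.
- A chi-squared test over 12 months does not test December and can be significant because of July alone.
- The primary hypothesis speaks of the period toward year end, so November's place is open.
- The Background says "Thus there may be potential for sicker and more complicated patients to undergo surgery at the end of the year". It does not settle whether that case mix is part of the December effect or a confounder, and no adjustment set is given.

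Comparator, endpoint and adjustment could therefore all be chosen after the data have been seen.

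**Working it through.** **The plan's own figure.** (9,000 + 15,000) cases per year × 2 years = 48,000, which matches the stated sample size. It is a count of available cases; the plan gives no power, alpha or event rate. Spread evenly, 48,000 / 12 = 4,000 per calendar month.

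**Assumptions.** Even spread, independent cases, two-sided 0.05. Baseline morbidity (10% or 5%) and the +1.4 point increase are assumed. The 18% relative increase is the only morbidity effect the Background quantifies, and it is for July-August against April-June. Applied here it gives 0.18 × 10% = 1.8 points and 0.18 × 5% = 0.9 points.

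**December against ten months (July left out), 10% and +1.4.**
- Pooled rate = (0.114 + 10 × 0.100) / 11 = 0.1013.
- Null SE = √[0.1013 × 0.8987 × (1/4,000 + 1/40,000)] = 0.00500.
- Alternative SE = √(0.114 × 0.886/4,000 + 0.100 × 0.900/40,000) = 0.00524.
- Power = Φ[(0.014 − 1.96 × 0.00500) / 0.00524] = 0.79. Simulation with 200,000 runs also gives 0.79.

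**December against eleven months, July also raised.** The reference mean rises by 1.4/11, so the difference shrinks to 1.4 × 10/11 = 1.27 points.

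**Simulated power for the comparisons (pooled two-proportion test or 11-df chi-squared).**

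| Baseline, increase | December v ten | December v eleven, July raised | 12-month chi-squared, December only |
|---|---|---|---|
| 10%, +1.4 | 0.79 | 0.71 | 0.41 |
| 10%, +1.8 (18% relative) | 0.94 | 0.89 | 0.65 |
| 5%, +0.9 (18% relative) | 0.68 | 0.60 | 0.32 |

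With equal month sizes, the chi-squared result is the same if July alone is raised, because the test does not know which month differs (0.41 in the first row). July in the comparator costs 0.08, 0.05 and 0.08 in the three rows.

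**Surge.** The Background says "Many physician practices notice a surge of patients seeking care at the end of the year". If December had 20% more cases than other months (size assumed; 48,000/12.2 = 3,934 per other month, 4,721 in December), the first row becomes 0.84, 0.77 and 0.47.

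**November (10%, +1.4).** If November is also raised, December against ten months falls to 0.70 (1.4 × 9/10 = 1.26 points). With November out of the reference it is 0.78. If November is not raised, removing it costs under 0.01.

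**Highest.** With January at 12.0%, December at 11.4% and the rest at 10% (assumed), the December-against-ten test is significant with probability 0.66, yet December is the top observed month in only 20% of runs.

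**Case mix (assumed).** Take morbidity of 16% in high-ASA and 6% in other patients, with a high-ASA share of 54% in December and 40% otherwise.
- December: 0.54 × 16% + 0.46 × 6% = 11.4%.
- Other months: 0.40 × 16% + 0.60 × 6% = 10.0%.
- The crude difference is 1.4 points; the within-stratum difference is 0.

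**The case against.** The strongest reply is that silence does not exclude a test. Date of surgery and complications are collected, a chi-squared test for categorical variables would cover month by complication, and a logistic model that includes month gives a December odds ratio. The word for highest in the primary hypothesis points towards December against the other months. A reader might infer that the plan cannot test, or will not test, its primary hypothesis. The documents do not support that; they show only that no test is specified.

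The effect sizes are also chosen. At the cited 18% relative increase, a December comparison has good power at a 10% baseline even with July in the comparator (0.89), so the power loss alone would be a modest matter. The figures further treat cases as independent, although there are only two Decembers and a reoperation could itself enter as a case. They use all main operating room procedures, and restricting to elective surgery, as the purpose has it, would lower every power.

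Finally, this is a short protocol for a retrospective chart review. It is dated 5-9-19, with analysis planned through December 2017. A reader might infer that choices were made after the results were seen. The documents do not say whether the analysis took place, so that inference is not supported either.

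What survives all of this is that the contrast, the outcome and the covariates are unstated, and no other section supplies them.

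**Conclusion.** The point stands as an omission in the analysis plan: neither the December nor the July hypothesis has a specified analysis. It rests on the text and does not depend on the simulations. Unnamed endpoints and covariates alone would be missing detail. The larger fault is that the only multivariable analysis is given a different purpose, prediction, when a simple association model would estimate both contrasts directly.

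Under the stated assumptions, leaving July in December's comparator costs about 5 to 8 percentage points of power. Relying on a 12-month chi-squared test costs far more (0.79 to 0.41, 0.94 to 0.65, 0.68 to 0.32) and does not identify December. The adjustment choice can matter more still: in the case-mix illustration it moves the December effect from 1.4 points to 0.

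**What to change.** Replace the prediction-model sentence with:

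> The main analysis is a logistic association model for any perioperative morbidity (yes/no), defined as any of: reoperation, 90-day readmission, 90-day death, excessive blood loss, transfusion, infection, thromboembolic event or organ injury. It has separate indicators for December, July and November; the other nine months are the reference. December is the primary test (two-sided 0.05); July is secondary. The unadjusted December effect carries the test, because it answers whether morbidity differs by time of year. The effect adjusted for age, BMI, ASA class, comorbidities, procedure type, hospital and year is reported beside it to show how much is case mix. Risk differences with 95% CIs are obtained by standardisation from the model. All 12 monthly rates are shown with CIs; a significant December term is read as above the reference months, not as highest. A sensitivity analysis returns November to the reference. Individual complications are descriptive, and any prediction model is separate.

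If the data have already been analysed, label this analysis post hoc; the text cannot undo earlier choices.

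**Cost.** SAP wording and a few model fits on data already planned for collection. Individual complications become descriptive. Two ungated tests give about a 10% chance of at least one false positive if neither month is raised (1 − 0.95² = 0.0975 for independent tests), which is why July stays secondary. Taking November out of the reference costs under 0.01 power. The components still need working definitions, since the protocol gives time windows only for readmission and death and no threshold for blood loss. The change does not settle the separate mismatch between elective surgery in the purpose and all main operating room procedures in the inclusion criteria.

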### **Ethical Considerations**

- **Informed consent**
  - Since this is a retrospective study, waivers of Informed Consent and Authorization will be requested.
- **Privacy information**
  - Patient surgery date and procedure will be collected during this study.

